8.7 Multiplicity

Formal statistical testing with associated p-value cut-offs centered around controlling Type-I error rates will not be used in assessing the hypotheses; hence no multiplicity adjustment is required or proposed.

8.8 Sample Size and Power Calculations

Pharmacodynamics (GIR_{max}):

The calculations in Table 11 below assume a between subject standard deviation of 0.44 for GIR_{max} , as was observed following SC administration of another IRPA (MK-5160) in healthy adult subjects. It is assumed that the variability of MK-1092 is similar to that of the other IRPA and that the variability in healthy adult subjects is similar to that in adult subjects with T1DM. The table below represents the probability of supporting the primary pharmacodynamics hypothesis under different assumed true mean of GIR_{max} values.

Table 11 Probability of Supporting Primary PD Hypothesis

| Target GIR_{max} (mg/kg/min) | True GIR_{max} | Probability of Supporting Hypothesis |
|--|------------------------------------|---|
| (1.5, 4.5) | 1 | 0.03% |
| | 1.5 | 30.9% |
| | 2 | 98.7% |
| | 2.5 | 100% |
| | 3 | 100% |
| | 3.5 | 100% |
| | 4 | 98.6% |
| | 4.5 | 29.40% |
| | 5 | 0.06% |

The calculations above were based on an assumed GIR_{max} standard deviation of 0.44 as observed in MK-5160 SC in P001, N=6 per dose, a posterior probability threshold of 70%, and 10,000 simulations.

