Dosing in all subsequent panels of Part 3 will commence upon review of the safety data from previous panels within Part 3 and determination of an acceptable safety profile to continue dose escalation. Up to 3 doses of MK-1092 will be administered in successive panels. The glargine dose will be the same in all panels of Part 3 and is expected to achieve $GIR_{max} \sim 2$ mg/kg/min. The MK-1092 doses will include, and may escalate beyond, the expected therapeutic insulin concentration range for a GIR_{max} of $\sim 1-2$ mg/kg/min. Doses in Part 3 will not exceed 64 nmol/kg SC, which is the highest planned dose in the clinical program. Different subjects will participate in each panel (N=6/panel receiving MK-1092, N=2/panel receiving glargine). The objectives for this part will assess safety and tolerability of the SC injection, PK, and PD endpoints for MK-1092 and glargine in adult subjects with T1DM.

Originally up to 4 doses of MK-1092 were planned for Part 3. However, per PCL #10 (dated 21-Mar-2018), Part 3 Panel I will not be conducted as it is anticipated that no more than 3 doses in Part 3 will be needed to assess the safety, PK and PD in subjects with T1DM, following review of data from Part 1. Additionally, an operational pause has been added between Panel H and Panel J in Part 3 only. The decision of whether to initiate Panel J will be made after thorough review of all available data from Panels G and H.

In Part 4, adult subjects with T2DM will be randomized to receive MK-1092 SC or glargine SC, as a single dose under the euglycemic clamp. Adult subjects with T2DM may use insulin as part of the pre-study regimen (*i.e.*, insulin-requiring T2DM) or may not use insulin as part of the pre-study regimen (*i.e.*, non-insulin-requiring T2DM).

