A summary of the observed GIR_{max} for the MK-1092 4.0 nmol/kg to 64 nmol/kg dose groups in Part 1 (NHV), for the MK-1092 8.0 nmol/kg and 32 nmol/kg dose group in Part 3 (T1DM), and for the 32 nmol/kg and 16 nmol/kg dose group in Part 4 (T2DM) are provided below. The GIR_{max} for all adult subjects randomized to glargine in any group of Part 1 (Panels A – E), Part 3 (Panel G and H), and Part 4 (Period 1 and 2) are also provided.

| Part 1 GIR_{max} values for MK-1092-001 (4-64 nmol/kg) and Glargine (3.0 nmol/kg), Part 3 GIR_{max} values for MK-1092-001 (8.0 nmol/kg and 32 nmol/kg) and Glargine (3.0 nmol/kg), and Part 4 GIR_{max} values for MK-1092-001 (16 nmol/kg and 32 nmol/kg) and Glargine (3.0 nmol/kg) | | |
|---|---------------------------------|--------------------------------------|
| | Dose | GIR_{max} (mg/kg/min) |
| Part 1 | MK-1092 4.0 nmol/kg | 0.9 |
| | MK-1092 8.0 nmol/kg | 1.7 |
| | MK-1092 16 nmol/kg | 3.1 |
| | MK-1092 32 nmol/kg | 3.3 |
| | MK-1092 64 nmol/kg | 4.4 |
| | Glargine 3.0 nmol/kg (0.5 U/kg) | 2.9 |
| | Part 3 | MK-1092 8.0 nmol/kg |
| MK-1092 32 nmol/kg | | 2.9 |
| Glargine 3.0 nmol/kg (0.5 U/kg) | | 2.5 |
| Part 4 | MK-1092 16 nmol/kg | 1.4 |
| | MK-1092 32 nmol/kg | 1.9 |
| | Glargine 3.0 nmol/kg (0.5 U/kg) | 1.2 |

In Part 1, a dose of 8.0 nmol/kg was safe, well-tolerated, and achieved GIR_{max} of ~1-2 mg/kg/min in healthy adult subjects. Therefore, this dose was tested with Humalog infusion in Part 2 in healthy adult subjects. In Part 2, all healthy subjects achieved GIR_{max} > 4 mg/kg/min. A dose of MK-1092 8.0 nmol/kg was therefore used as the initial dose in Part 3 (adult subjects with T1DM). After 8.0 nmol/kg was tested in Part 2, subsequent panels in Part 1 testing up to 64 nmol/kg have been resumed. A dose of 32 nmol/kg was used as the initial dose in Part 4 (adult subjects with T2DM). A dose of 16 nmol/kg was used as the second dose in Part 4 so as to explore the PD effects of doses below 32 nmol/kg. These doses have been safe and well-tolerated.

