In Part 2, four healthy adult subjects will be administered a SC dose of MK-1092. The glycemic effect of IV Humalog following SC administration of MK-1092 will be examined in the single panel of this part. The dosing level of MK-1092 8.0 nmol/kg was determined from data in Part 1, and was communicated with the site by a Protocol Clarification Letter prior to the dosing in Part 2. Subjects will receive MK-1092 at a dose expected to lead to a GIR ~1-2 mg/kg/min. Subjects will also receive a 3 hr infusion of Humalog 1.2 nmol/kg IV (0.2 units/kg) at approximately 12 hr after SC administration of MK-1092, a time at which MK-1092 is anticipated to have a glycemic effect. The actual start time of Humalog infusion was confirmed as 12 h post-dose in a Protocol Clarification Letter prior to the dosing in Part 2. As in Part 1, the GIR will be adjusted as necessary to maintain the pre-specified blood glucose level and subjects will remain on the euglycemic clamp until the GIR has stabilized near 0 mg/kg/min and glucose infusion can be discontinued safely, at the discretion of the investigator.

In Part 3, six adult subjects with T1DM will be administered a SC dose of MK-1092 and two adult subjects with T1DM will be administered a SC dose of glargine 3.0 nmol/kg (0.5 units/kg) in each panel. The dose in Panel G will be determined following review of data from Part 1 and will be no higher than a safe and tolerated dose that achieves GIR ~1-2 mg/kg/min (Part 1) and has been tested with Humalog infusion (Part 2) in healthy adult subjects. As of the timing of amendment 03, the dose of 8.0 nmol/kg had fulfilled these requirements and was tested in Part 3 Panel G. Decisions to increase, decrease, or repeat SC dosing levels in Part 3 will be based primarily on safety and tolerability data from prior panels in Part 3, and doses may be increased up to the planned maximum clinical dose of 64 nmol/kg SC. The dose of Part 3 Panel G was communicated to the site by Protocol Clarification Letter prior to dosing.

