8.6 Statistical Methods

Primary

Safety (All Study Parts):

Incidence of adverse experiences will be descriptively summarized. Summary statistics and plots will be generated for the change from baseline values in the vital signs, ECG parameters, and selected laboratory safety parameters for subjects, as deemed clinically

appropriate. Depending on the safety parameter, the difference from baseline will either be computed on the original scale (raw change from baseline) or on the log scale and back-transformed for reporting (percent change from baseline). Summary statistics for the raw laboratory safety tests, ECGs, and/or vital signs may also be computed, as deemed clinically appropriate.

Pharmacodynamics:

GIR (Part 3)

Individual maximal GIR_{max} during the euglycemic clamp timeframe following MK-1092 SC or glargine SC administered to adult subjects with T1DM based on LOESS smoothed data from Part 3 will be analyzed in a fixed effects model with an effect for treatment (i.e. glargine dose, MK-1092 Dose Level 1, MK-1092 Dose Level 2, etc). Means and 95% confidence intervals of GIR_{max} for each treatment/dose will be calculated from the model. To test the Part 3 primary hypothesis, the posterior probability that the true mean GIR_{max} level is within 1.5 and 4.5 mg/kg/min will be calculated for each MK-1092 dose using a non-informative prior. If this posterior probability exceeds 70% for at least one safe and well tolerated dose of MK-1092 SC then the primary research hypothesis for Part 3 will be supported.

Additionally, a non-linear mixed effects model-based analysis may be used to assess the PK/PD (i.e. concentration/GIR) relationship. The model for MK-1092 will be developed using data from Part 3. The model for glargine will be developed using data from Part 3 of the current study and available historical data.

Secondary

Pharmacodynamics:

GIR (Parts 1 & 4):

Individual maximal GIR values (GIR_{max}) during the clamp in Part 1 and Part 4 will be smoothed based on LOESS method.

Model based (similar to Part 3: fixed effect model) statistics such as means, 95% confidence intervals etc. will be provided for each treatment/dose in Part 1.

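### Tables 10 and 11 are labelled as the probability of supporting the primary PD hypothesis but hold per-dose figures; under the any-dose rule the boundary value runs from about 30% to a worst case of about 66%

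*Combined protocol and SAP*

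**What the plan says.** The decision rule is in Section 8.6 (and in summary in Section 8.1). A posterior probability that the true mean GIRmax lies between 1.5 and 4.5 mg/kg/min is computed separately for each MK-1092 dose. Then, in Part 3: "If this posterior probability exceeds 70% for at least one safe and well tolerated dose of MK-1092 SC then the primary research hypothesis" counts as supported.

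Section 2.1 says of Part 3: "Up to 3 doses of MK-1092 will be administered in successive panels". Each panel uses different subjects, six of them on MK-1092. Panel I is omitted and Panel J is optional: "The decision of whether to initiate Panel J will be made after thorough review of all available data from Panels G and H". Two or three doses will therefore feed the rule.

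Section 8.8 introduces Table 11 with "The table below represents the probability of supporting the primary pharmacodynamics hypothesis under different assumed true mean of" GIRmax. The table title and column heading also refer to support for the hypothesis. Each row has one true mean. The footnote gives the settings as SD 0.44, "N=6 per dose, a posterior probability threshold of 70%, and 10,000 simulations". Table 10 in Section 8.1 carries the same entries, text and footnote.

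**The concern.** Under an any-dose rule, the chance of supporting the hypothesis depends on the true means of all the doses tested. A column indexed by a single true mean can describe the hypothesis only if one dose is tested, or if all doses but one have practically no chance of passing. Neither table says so, and no figure is given for two or three doses.

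These tables are the only operating characteristics given for the primary PD hypothesis. A reader who takes the boundary rows at face value would conclude that a compound whose mean GIRmax only just reaches the edge of the window is declared successful about 30% of the time. If two or three doses lie near that edge, the chance is higher, and the tables do not show by how much.

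**Working it through.** **Inputs.** SD 0.44 mg/kg/min, N = 6 per dose, threshold 70% (Section 8.8). Window 1.5 to 4.5 mg/kg/min (Section 8.3). Separate posterior per dose with a non-informative prior, any-dose rule (Section 8.6). Up to three doses in different subjects (Section 2.1).

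**Step 1: reproduce the tables for one dose.** The standard error of a dose mean is 0.44/√6 = 0.180. With a flat prior and known SD, the far limit of the window is negligible near the lower boundary, so a dose with true mean μ passes with probability about Φ((μ − 1.5)/0.180 − 0.524), where 0.524 is the 70th percentile of the standard normal. At μ = 1.5 this is Φ(−0.524) = 30%. Simulation with the SD estimated in the dose group (t posterior, 5 df) gives:

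| True mean | Tables 10 and 11 | One dose, recomputed |
|---|---|---|
| 1.0 | 0.03% | 0.06% |
| 1.5 | 30.9% | 30.0% |
| 2.0 | 98.7% | 98.7% |
| 2.5 to 3.5 | 100% | 100% |
| 4.0 | 98.6% | 98.7% |
| 4.5 | 29.4% | 30.0% |
| 5.0 | 0.06% | 0.05% |

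The largest difference is 0.9 points. With 10,000 simulations the standard error of the 30.9% entry is √(0.309 × 0.691/10,000) = 0.46 points, so simulation noise is enough to explain it. The tables are single-dose results.

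**Step 2: apply the rule as written.** For independent doses with per-dose probabilities p₁, p₂, …, the chance that at least one passes is 1 − (1 − p₁)(1 − p₂)….

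- Two doses on a boundary: 1 − 0.7² = 51.0%.
- Three doses on a boundary: 1 − 0.7³ = 65.7%. Joint simulation gives 65.4% to 65.8%, whether the SD is taken as known, estimated per dose or pooled across treatments.
- From the tables' own entries, three doses give 1 − 0.691³ = 67.0% at 1.5 and 1 − 0.706³ = 64.8% at 4.5.

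**Step 3: other dose profiles.** The first two rows below scale the Part 1 GIRmax values in Section 4.1.2 (8, 16, 32 and 64 nmol/kg: 1.7, 3.1, 3.3 and 4.4) so that the highest mean equals 1.5. The remaining rows are assumed profiles.

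| True means | Basis | Any-dose support |
|---|---|---|
| 0.58, 1.12, 1.5 | 8, 32, 64 nmol/kg × 1.5/4.4 | 30.4% |
| 0.77, 1.41, 1.5 | 8, 16, 32 nmol/kg × 1.5/3.3 | 40.6% |
| 1.0, 1.25, 1.5 | assumed | 32.0% |
| 1.3, 1.4, 1.5 | assumed | 43.1% |
| 1.4, 1.4 | assumed (14% per dose) | 26.2% |
| 1.4, 1.4, 1.4 | assumed (14% per dose) | 36.7% |
| 2.0, 2.0, 2.0 | assumed (98.7% per dose) | about 100% |
| 1.0, 1.0, 1.0 | assumed (0.06% per dose) | 0.17% |

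**The case against.** The best reply is that the entries contain no error and that a careful reader would take them as per dose: each row has one mean, the footnote gives the sample size per dose, and Section 8.6 computes the posterior dose by dose. But the footnote says how many subjects each dose has, not what event the probability refers to, while the title, introduction and column heading all name the hypothesis.

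Second, 66% is a corner case. It needs Panel J to run, three distinct dose levels all judged safe and tolerated, and all three true means on a boundary. That is right. The Part 1 dose-response rises, and scaling it at 8, 32 and 64 nmol/kg leaves the boundary figure at about 30%. Means close together are still plausible: Part 1 gave 3.1 and 3.3 at 16 and 32 nmol/kg, and Section 4.1.1 describes a flatter dose-response with an attenuated maximum in animal models. Repeating a dose level, which Section 4.2.2.4 allows, would not add a second chance. The model's effects are dose levels, so the repeat would naturally pool to N = 12 and still pass about 30% of the time at the boundary.

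Third, Section 8.7 disclaims type I error control and no limit on false support is set, so no promised property is broken. That also stands, and no multiplicity adjustment is asked for. It does not turn a per-dose figure into a hypothesis-level one.

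Finally, the preliminary 32 nmol/kg value in Part 3 is 2.9. If that is the mean of six subjects with SD 0.44, the posterior probability for that dose is about 99.96%. This limits the consequence for the trial's conclusion but does not correct the tables.

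**Conclusion.** The concern holds. Tables 10 and 11 report the chance that one dose of six subjects passes, under a label that promises the chance of supporting a hypothesis decided by an any-dose rule. At the boundary the probability under the rule as written is about 30% with one dose there and the others well outside, 51% with two doses there, and about 66% with three. The last is an upper limit over profiles with no mean inside the window, not an expected value; if Panel J is not run, the limit is 51%.

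These figures assume SD 0.44, six subjects per dose, a flat prior, independent panels, and every dose judged safe and tolerated. The gap is concentrated near 1.5 and 4.5: it is negligible well outside the window, and inside it the tables err slightly on the conservative side. The Part 3 conclusion is unlikely to change.

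**What to change.** In Tables 10 and 11, relabel the probability column as per dose and amend the introductory sentence to match. Add the probability that at least one of two, and at least one of three, doses passes, for a few stated profiles: flat, rising as in Part 1, and plateau. Present about 66% explicitly as the worst case. Leave the 70% threshold unchanged.

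The cost is a short simulation, one column label and a few rows in two tables. The decision rule, the number of subjects and the conduct of the trial are unaffected.

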9.0 LABELING, PACKAGING, STORAGE AND RETURN OF CLINICAL SUPPLIES

9.1 Investigational Product

The investigator shall take responsibility for and shall take all steps to maintain appropriate records and ensure appropriate supply, storage, handling, distribution and usage of investigational product in accordance with the protocol and any applicable laws and regulations.

Clinical Supplies will be provided by the Sponsor as summarized in [Table 12](#).

Clinical supplies will be packaged to support enrollment and replacement subjects as required. When a replacement subject is required, the Sponsor or designee needs to be contacted prior to dosing the replacement supplies.

Table 12 Product Description

| Product Name & Potency | Dosage Form | Source/Additional Information |
|-----------------------------------|---|--------------------------------------|
| MK-1092, 20.0 mg/mL | Sterile Solution for Injection, 1.0 mL per vial | Supplied by Sponsor |

All supplies indicated in [Table 12](#) will be provided per the “Source/Additional Information” column depending on local country operational requirements.

Any commercially available product not included in [Table 12](#) will be provided by the trial site, subsidiary or designee. Every attempt should be made to source these supplies from a single lot/batch number. The trial site is responsible for recording the lot number, manufacturer, and expiry date for any locally purchased product as per local guidelines unless otherwise instructed by the Sponsor.

9.2 Packaging and Labeling Information

Clinical supplies will be affixed with a clinical label in accordance with regulatory requirements.

Subjects will receive open label vials. No kitting is required.

9.3 Clinical Supplies Disclosure

Part 2 of the trial is open-label; therefore, the subject, the trial site personnel, the Sponsor and/or designee are not blinded. Treatment (name, strength or potency) is included in the label text; random code/disclosure envelopes or lists are not provided.

Part 1, Part 3 and Part 4 of this trial are blinded but supplies are provided open label; therefore, an unblinded pharmacist or qualified trial site personnel will be used to blind supplies. Treatment identity (name, strength or potency) is included in the label text; random code/disclosure envelopes or lists are not provided.

The emergency unblinding call center will use the treatment allocation/randomization schedule for the trial to unblind subjects and to unmask treatment identity for this trial. The Sponsor will not provide random code/disclosure envelopes or lists with the clinical supplies.

9.4 Storage and Handling Requirements

Clinical supplies must be stored in a secure, limited-access location under the storage conditions specified on the label.

Receipt and dispensing of trial medication must be recorded by an authorized person at the trial site.

Clinical supplies may not be used for any purpose other than that stated in the protocol.

9.5 Discard/Destruction>Returns and Reconciliation

The investigator is responsible for keeping accurate records of the clinical supplies received from the Sponsor or designee, the amount dispensed to and returned by the subjects and the amount remaining at the conclusion of the trial. For all trial sites, the local country Sponsor personnel or designee will provide appropriate documentation that must be completed for drug accountability and return, or local discard and destruction if appropriate. Where local discard and destruction is appropriate, the investigator is responsible for ensuring that a local discard/destruction procedure is documented.

10.0 ADMINISTRATIVE AND REGULATORY DETAILS

10.1 Confidentiality

10.1.1 Confidentiality of Data

By signing this protocol, the investigator affirms to the Sponsor that information furnished to the investigator by the Sponsor will be maintained in confidence, and such information will be divulged to the institutional review board, ethics review committee (IRB/ERC) or similar or expert committee; affiliated institution and employees, only under an appropriate understanding of confidentiality with such board or committee, affiliated institution and employees. Data generated by this trial will be considered confidential by the investigator, except to the extent that it is included in a publication as provided in the Publications section of this protocol.

10.1.2 Confidentiality of Subject Records

By signing this protocol, the investigator agrees that the Sponsor (or Sponsor representative), IRB/ERC, or regulatory authority representatives may consult and/or copy trial documents in order to verify worksheet/case report form data. By signing the consent form, the subject agrees to this process. If trial documents will be photocopied during the process of verifying worksheet/case report form information, the subject will be identified by unique code only; full names/initials will be masked prior to transmission to the Sponsor.

By signing this protocol, the investigator agrees to treat all subject data used and disclosed in connection with this trial in accordance with all applicable privacy laws, rules and regulations.

10.1.3 Confidentiality of Investigator Information

By signing this protocol, the investigator recognizes that certain personal identifying information with respect to the investigator, and all subinvestigators and trial site personnel, may be used and disclosed for trial management purposes, as part of a regulatory submissions, and as required by law. This information may include:

1. name, address, telephone number and e-mail address;
2. hospital or clinic address and telephone number;
3. curriculum vitae or other summary of qualifications and credentials; and
4. other professional documentation.

Consistent with the purposes described above, this information may be transmitted to the Sponsor, and subsidiaries, affiliates and agents of the Sponsor, in your country and other countries, including countries that do not have laws protecting such information. Additionally, the investigator's name and business contact information may be included when reporting certain serious adverse events to regulatory authorities or to other investigators. By signing this protocol, the investigator expressly consents to these uses and disclosures.

If this is a multicenter trial, in order to facilitate contact between investigators, the Sponsor may share an investigator's name and contact information with other participating investigators upon request.

10.1.4 Confidentiality of IRB/IEC Information

The Sponsor is required to record the name and address of each IRB/IEC that reviews and approves this trial. The Sponsor is also required to document that each IRB/IEC meets regulatory and ICH GCP requirements by requesting and maintaining records of the names and qualifications of the IRB/IEC members and to make these records available for regulatory agency review upon request by those agencies.

